7.1. Discontinuation of Study Treatment

Events that will result in discontinuation of study treatment include:

- Inability to tolerate either study treatment secondary to perceived or observed side effects.
- Pregnancy (not due to safety reasons but because pregnancy may interfere with the primary endpoint)
- Any other changes to clinical signs or changes in laboratory values, physical status or AEs that could compromise the participant's status if they were to continue with the study treatment or if the Investigator feels that it is not in the best interests of the participant.

If a participant shows persistent signs of under-replacement on the starting dose of 30 mg Chronocort or IRHC they will be monitored and if symptoms do not resolve the participant should be withdrawn from study treatment. If a participant shows persistent signs of under-replacement during the titration period and has received at least 1 down titration of 5 mg, a reversion to the previous dose is permitted (i.e. an increase of 5 mg) after discussion with the medical monitor. If symptoms persist, no further dose increases can be made, and the participant should be withdrawn from study treatment (such cases should be discussed with the medical monitor).

If a participant discontinues study treatment, they should be placed onto the previous glucocorticoid treatment and dose they were receiving prior to entry into this study. They should complete as many of the assessments scheduled for Visit 6 as possible, preferably within 48 hours of stopping study treatment. In all cases except pregnancy (see Section 8.4.5 for handling of any pregnancies) the participant should be kept in the study, if the participant consents to this, and all further safety assessments conducted in line with the protocol schedule (note: no efficacy endpoints will be collected once the assessments detailed for Visit 6 [early withdrawal] are completed). The date the participant discontinues study treatment and the reason for discontinuation will be recorded on the participant's eCRF. Participants who have been randomized to study treatment and who discontinue from study treatment are not to be replaced. The handling of safety data collected after the participant has discontinued study treatment will be detailed in the SAP.

Participants who discontinue study treatment are not eligible to enter the long-term extension study (DIUR-015), except in the case of pregnancy (see Section 8.4.5).

7.2. Participant Discontinuation/Withdrawal from the Study

A participant may withdraw from the study at any time at his/her own request without stating a reason and without prejudice to further treatment, or may be withdrawn at any time at the discretion of the Investigator for safety, behavioral, compliance, or administrative reasons. Participants who become pregnant must be withdrawn from the study (see Section 8.4.5).

If the participant withdraws consent for disclosure of future information, the Sponsor may retain and continue to use any data collected before such a withdrawal of consent. The

participant may also request destruction of any samples taken and not tested, and the Investigator must document this in the site study records.

If at the baseline visit the participant has had persistent signs of adrenal insufficiency or they have not tolerated the 4-week run-in medication, they should be withdrawn from the study at this point before randomization.

If a participant discontinues from the study prior to the last scheduled visit, all efforts should be made to perform the EOS assessments (as per Visit 6) at the point the participant withdraws from the study (at the latest within 48 hours of the last dose of study medication). In particular, the androgen measurements should be taken if possible.

Participants who discontinue from the study are not eligible to enter the long-term extension study (DIUR-015) except in the case of pregnancy (see Section 8.4.5).

7.3. Lost to Follow-up

A participant will be considered lost to follow-up if he/she repeatedly fails to return for scheduled visits and is unable to be contacted by the study site. The following actions will be taken if a participant fails to return to the clinic for a required study visit:

- The site must attempt to contact the participant and re-schedule the missed visit as soon as possible and counsel the participant on the importance of maintaining the assigned visit schedule and ascertain whether or not the participant wishes to and/or should continue in the study.
- Before a participant is deemed lost to follow-up, the Investigator or designee must make every effort to regain contact with the participant (where possible, 3 telephone calls and, if necessary, a certified letter to the participant's last known mailing address or local equivalent methods). These contact attempts should be documented in the participant's medical record.
- Should the participant continue to be unreachable, he/she will be considered to have withdrawn from the study at the time of their last assessment, with a primary reason of lost to follow-up.

Discontinuation of specific sites or of the study as a whole are detailed in Appendix 1.

8. Study Assessments and Procedures

- Study procedures and their timing are summarized in the Schedule of Activities (SoA) (Section 1.3). Protocol waivers or exemptions are not allowed.
- Immediate safety concerns should be discussed with the Sponsor and the medical monitor immediately upon occurrence or awareness to determine if the participant should continue or discontinue study treatment.
- Adherence to the study design requirements, including those specified in the SoA (Section 1.3), is essential and required for study conduct.
- All screening evaluations must be completed and reviewed to confirm that potential participants meet all eligibility criteria. The Investigator will maintain a screening log to record details of all participants screened and to confirm eligibility or record reasons for screening failure, as applicable.
- Procedures conducted as part of the participant's routine clinical management (e.g. blood count) and obtained before signing of the ICF may be utilized for screening or baseline purposes provided the procedures met the protocol-specified criteria and were performed within the time-frame defined in the SoA (Section 1.3).
- At any visit, if multiple assessments are being conducted, vital signs should be conducted before any blood tests, and blood samples for androgen testing and optional saliva samples for salivary steroid profile must be conducted prior to any dosing. All other assessments should be conducted between the 08:00 and 13:00 androgen sampling points, where possible.
- If a visit has to be moved (e.g. due to use of 'stress dosing rules'), the participant should return to their usual visit schedule as soon as possible (i.e. all subsequent visits should not be moved out as well).
- In some cases (e.g. if the participant lives a long way from the study site or if pandemic guidelines dictate) study visits 3 and 4 may be performed as domiciliary visits and IMP shipments can be made directly to the participant's home. However, the following visits must be performed at the study site: Screening (Visit 1), Baseline (Visit 2), Week 16 (Visit 5), and EOS/early withdrawal visit (Visit 6). If necessary in some cases, IMP at Visit 5 can also be delivered to the participant's home. If a domiciliary visit is conducted the safety and endocrine blood samples must be sent to the central laboratory for analysis and the Investigator must complete the adrenal insufficiency checklist. The assessment of hirsutism and acne can be conducted via a video call (within ± 2 days of the domiciliary visit). If androgen samples are analyzed locally for safety reasons the participant must be withdrawn from treatment.
- If a participant discontinues treatment early (see Section 7.1), the assessments scheduled for Visit 6 (end of treatment) should be conducted, if possible, preferably within 48 hours of stopping study treatment. The participant should be kept in the study, if the participant consents to this, and all further safety assessments conducted in line with the protocol schedule (note: no efficacy endpoints will be collected once the assessments detailed for Visit 6 [early withdrawal] are completed).

8.1. Study Visits

8.1.1. Visit 1 (Screening Visit - Week -4)

Four weeks prior to the baseline visit, participants will be requested to attend the study site for the screening visit (it is mandatory that this visit is conducted at the study site). Prior to the visit, the site staff should contact the participant to check that they have been receiving their usual CAH medication and 'stress dosing rules' have not been applied in the 5 days preceding the visit date. If the 'stress dosing rules' have been applied, then the visit should be postponed until the participant has been receiving their usual CAH medication for 5 days. The participant will be told to take their CAH medication at the usual times throughout the visit. The ICF should be given to the participant at least 24 hours before the screening visit, along with the Investigator's contact details, so that each participant has sufficient time to read the information and ask any questions they may have. If necessary, at Visit 1 the ICF can be reviewed again with the participant and the participant given ample opportunity to ask any questions before they are asked to sign it. The ICF must be signed at or before Visit 1 and prior to any study related procedures.

Minors will be assented, and parental consent sought in keeping with USA and EU laws and local Independent Ethics Committee (IEC) or Institutional Review Board (IRB) requirements. Minors will be re-consented on reaching the age of majority if still participating in the study at that time.

The following assessments will be carried out and recorded at this visit:

- All inclusion and exclusion criteria checked
- Demographic data
- Medical history taken (including menstrual history, menopausal status and oral contraception use in female participants)
- Details on concomitant medications taken (CAH medication will be recorded separately from other concomitant medications)
- Signs and symptoms of adrenal insufficiency using the adrenal insufficiency checklist
- Height, weight, and waist circumference will be measured
- Full physical examination
- Vital signs (BP, heart rate [HR], respiratory rate and body temperature). BP to be recorded after the participant has been semi-supine for 10 minutes.
- Urine sample for urinalysis
- Blood samples will be taken for routine biochemistry and hematology
- Sample taken for PRA or PRC, preferably after the participant has been supine for 30 minutes
- Blood sample taken for HbA1c
- Pregnancy test in WOCBP (either urine or blood as per the site's usual practice)
- Record the details of the participant's glucocorticoid doses for the previous 24 hours and throughout the visit.
- Recording of any AEs since informed consent/assent was taken.
- Blood sampling for measurement of androgen levels (17-OHP and A4)

The participants will be told not to take their morning dose of IRHC before attending for the visit (the morning dose will be taken after the 08:00 hour androgen sample). The androgen

sampling will commence at 08:00 hours, with 1 other sample taken at 13:00 hours. These blood samples are to be taken within \pm 30 minutes of the stated timepoints, with the exact sampling times recorded in the eCRF. Half the sample will be sent to the central laboratory for analysis, with the remaining half initially retained at the site before being sent to the central laboratory and then on to the biobank for long-term storage and possible future research. Participants will then be switched to the run-in medication, which will comprise 20 mg IRHC in the morning on waking (typically between 06:00 and 08:00 hours) and 10 mg in the afternoon (between 15:00 and 17:00 hours) for the next 4 weeks. Once the last blood sample has been taken at 13:00 hours and all other assessments have been completed, the participant will be allowed home, and instructed to take their first dose of run-in medication later that afternoon (between 15:00 and 17:00 hours). The participant will also be issued with an emergency treatment pack to be used in the event of illness and implementation of ‘stress dosing rules’ (Section 6.1.1). The participant will be asked to return to the clinic in 4 weeks’ time for the baseline visit (Visit 2).

8.1.2. Visit 2 (Baseline Visit - Day 1: 4 Weeks After the Screening Visit)

Prior to the visit, the site staff should contact the participant to check that ‘stress dosing rules’ have not been applied in the 5 days preceding the visit date. If ‘stress dosing rules’ have been applied, then the visit should be postponed until the participant has been receiving only the run-in IRHC medication for 5 days. It is mandatory that this visit is conducted at the study site. The participant will be instructed to bring any empty packaging and any unused run-in medication and the emergency treatment pack with them to the visit for accountability purposes (note: participants take unused study medication and emergency treatment pack back home with them to use until the dose titration decision is made and new study medication dispensed). The participants will be told not to take their morning dose of IRHC before attending for the visit (the morning dose will be taken after the 08:00 hour androgen sample and optional saliva sample [where applicable]). Male participants will be asked not to take multivitamins or dietary supplements containing biotin or vitamin B7 for 12 hours prior to the visit (to avoid interference with LH test results) and also not to ejaculate for the preceding 3 days for the sperm count assessment (if the participant has consented to this assessment). If the participant has had persistent signs of adrenal insufficiency or they have not tolerated the 4-week run-in medication, they should be withdrawn from the study at this point before randomization.

The following assessments will be carried out and recorded at this visit:

- Limited check of inclusion/exclusion criteria
- Record the details of the participant’s glucocorticoid doses for the previous 24 hours and throughout the visit
- Participants will be asked about any AEs and concomitant medications changes since the last visit
- Vital signs (BP, HR, respiratory rate and body temperature. BP to be recorded after the participant has been semi-supine for 10 minutes)
- Full physical examination
- Height, weight, and waist circumference will be measured
- Assessment of menstrual cycle changes in all pre-menopausal women

- Assessment of hirsutism by female participants using a VAS and by Investigators using Ferriman-Gallwey score
- Assessment of acne by female participants using a VAS and by Investigators using the GEA
- Assessment of alertness by the participant using a VAS
- Signs and symptoms of adrenal insufficiency using the adrenal insufficiency checklist
- The following questionnaires will be completed: SF-36®, MAF, and EQ-5D-5L™
- ECG
- TART measured by ultrasound in male participants (results read by central laboratory)
- Sperm count measured at home using a testing kit supplied to the male participants (only in participants who have consented to this assessment)
- Urinalysis
- Blood sample for FSH, osteocalcin, LH, 11-ketotestosterone, total testosterone, DHEA, and routine biochemistry and hematology
- Pregnancy test in WOCBP (either urine or blood as per the site's usual practice)
- Review of returned run-in medication and emergency treatment pack for compliance
- Blood sampling for measurement of androgen levels (17-OHP and A4) at 08.00 (pre-dose) and 13.00 hours
- Saliva samples collected for exploratory analysis at 08.00 (pre-dose) and 13.00 hours (optional).

The androgen blood samples are to be taken within \pm 30 minutes of the stated timepoints, with the exact sampling times recorded in the eCRF. Half the sample will be sent to the central laboratory for analysis, with the remaining half initially retained at the site before being sent to the central laboratory and then on to the biobank for long-term storage and possible future research. Once the participant's eligibility for the study has been confirmed, the participant will be randomized via the IRT to either Chronocort or to continue with IRHC. The IRT will take into account the participant's fludrocortisone replacement status (requires fludrocortisone or does not require fludrocortisone). Participants randomized to Chronocort will change to a dosing regimen of 10 mg in the morning on waking (typically between 06:00 and 08:00 hours) and 20 mg at night just prior to going to bed (typically between 22:00 hours and midnight) whereas participants randomized to IRHC will continue the same dosing regimen as they were receiving during the run-in period (20 mg in the morning on waking [typically between 06:00 and 08:00 hours] and 10 mg in the afternoon [between 15:00 and 17:00 hours]). Placebo capsules will also be provided to maintain the study blinding. The participant will be dispensed with the correct active and placebo study medication and an emergency treatment pack in case they need to implement 'stress dosing rules', and then they will be allowed home. Participants will be instructed to take their first dose of study medication that afternoon. Participants will be asked to record the dose, date and time they took the first dose of study medication (Chronocort or IRHC) in their electronic participant diary.

Participants will be given an electronic participant diary and will be instructed what to record in it. In particular, they will be instructed to complete the alertness VAS on a weekly basis in the morning before their morning dose of study medication. The same day of the week should

be used each week. The participant will be asked to attend the clinic for Visit 3 in 4 weeks' time.

8.1.3. Visit 3 (Titration Visit - Week 4 + 1 Week)

Four weeks after the previous visit (+ 1 week), the participant will be requested to attend the study site for testing of androgen levels (if necessary this visit can be conducted as a domiciliary visit). Prior to the visit, the site staff should contact the participant to check that 'stress dosing rules' have not been applied in the 5 days preceding the visit date. If 'stress dosing rules' have been applied, then the visit should be postponed until the participant has been receiving no stress dosing medication for 5 days. The participant will be instructed to bring any empty packaging and any unused study medication and the emergency treatment pack with them to the visit for accountability purposes (note: participants take unused study medication and emergency treatment pack back home with them to use until the dose titration decision is made and new study medication dispensed). The participants will be told not to take their morning dose of study medication before attending for the visit (the morning dose will be taken after the 08:00 hour androgen sample and optional saliva sample [where applicable]). Male participants will be asked not to take multivitamins or dietary supplements containing biotin or vitamin B7 for 12 hours prior to the visit (to avoid interference with LH test results).

The following assessments will be carried out and recorded at this visit:

- Record the details of the participant's glucocorticoid doses for the previous 24 hours and throughout the visit
- Participants will be asked about any AEs (including events considered to be of unexpected benefit) and concomitant medications changes since the last visit
- Vital signs (BP, HR, respiratory rate and body temperature. BP to be recorded after the participant has been semi-supine for 10 minutes)
- Abbreviated physical examination (if indicated by AEs)
- Height, weight, and waist circumference will be measured
- Assessment of menstrual cycle changes in all pre-menopausal women
- Assessment of hirsutism by female participants using a VAS and by Investigators using Ferriman-Gallwey score (the Investigator can assess this via a video call if a domiciliary visit is conducted for this visit [within ±2 days of the domiciliary visit])
- Assessment of acne by female participants using a VAS and by Investigators using the GEA (the Investigator can assess this via a video call if a domiciliary visit is conducted for this visit [within ±2 days of the domiciliary visit])
- Assessment of alertness by the participant using a VAS
- Signs and symptoms of adrenal insufficiency using the adrenal insufficiency checklist (the Investigator must complete the checklist even if a domiciliary visit is conducted for this visit)
- The following questionnaires will be completed: SF-36®, MAF, and EQ-5D-5L™
- Blood sample for HbA1c, FSH, osteocalcin, LH, and routine biochemistry and hematology
- Urinalysis
- Pregnancy test in WOCBP (either urine or blood as per the site's usual practice)
- Review of emergency treatment pack for compliance

- Blood sampling for measurement of androgen levels (17-OHP and A4) at 08.00 (pre-dose) and 13.00 hours
- Saliva samples collected for exploratory analysis at 08.00 (pre-dose) and 13.00 hours (optional).

The androgen blood samples are to be taken within ± 30 minutes of the stated timepoints, with the exact sampling times recorded in the eCRF. Half the sample will be sent for analysis at the central laboratory, with the remaining half initially retained at the site before being sent to the central laboratory and then on to the biobank for long-term storage and possible future research.

The participant will be asked to attend the clinic for Visit 4 in 6 weeks' time. Participants will be reminded to complete the alertness VAS on a weekly basis in the morning before their morning dose of study medication. The same day of the week should be used each week. Participants will be discharged once the last androgen sample has been taken and all other assessments have been completed.

Following determination of the Visit 3 androgen levels and completion of the adrenal insufficiency checklist, a decision will be made by an independent blinded physician as to whether the participant's dose should be adjusted, and the appropriate IMP packs will be sent to the participant, either to collect from their local study site or sent directly to the participant's home (note: the changes will also include the relevant changes to the placebo capsules to maintain the blinding). The treatment packs for each participant will always contain the same number of capsules as the previous supplies (with placebo capsules masking any changes), thus ensuring the participant is not aware of any dose changes. Participants will be asked to record the dose, date and time they took the first dose of the revised study medication (if applicable) in their electronic participant diary.

Any dose titrations should be made within 2 to 3 weeks of the visit (dependent on the laboratory turnaround time of androgen samples, the time needed by the independent blinded physician to evaluate the data, and for the supplies to be sent to the participant).

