of the reference range), then the dose will be adjusted down by a total of 5 mg. If one or both androgen results are above these limits, then no titration will be undertaken. Clinical symptoms of adrenal insufficiency on the adrenal insufficiency checklist should take precedence over androgen results and would inhibit titration. Only 1 of the 2 doses a participant receives (i.e. morning or afternoon/evening) should be titrated at each titration point but no dose should be reduced below 5 mg. If the androgen results indicate that both doses should be reduced, then precedence should be given to reducing the morning dose of Chronocort and the afternoon dose of IRHC. If the same situation then recurs at the next titration timepoint then the dose reduced should be alternated to avoid a mismatch of dosing. Each treatment arm will be subject to the same titration rules throughout the study, ensuring that opportunities for optimization and control of androgens are the same in both arms and thus minimizing bias in the management of participants. These androgen precursor limits have been defined based on data from previous studies in the clinical development program.

If a participant shows persistent signs of under-replacement on the randomized starting dose of 30 mg Chronocort or IRHC they will be monitored and if symptoms do not resolve the participant should be withdrawn from treatment and given alternative therapy at the Investigator's discretion. If a participant shows persistent signs of under-replacement during the titration period and the participant has received at least 1 down titration of 5 mg, a reversion to the previous dose is permitted (i.e. an increase of 5 mg) after discussion with the medical monitor. If symptoms persist, no further dose increases can be made, and the participant should be withdrawn from study treatment (such cases should be discussed with the medical monitor). If the Investigator thinks that the dose needs to be adjusted between visits, they should contact the medical monitor to discuss the case. For emergency situations, the emergency treatment pack can be used, and the medical monitor should be contacted as soon as possible.

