6.3. Measures to Minimize Bias: Randomization and Blinding

This is a double-blinded study with 2 treatment arms. The blinded treatment to be taken by a participant will be assigned using an IRT on a 1:1 basis (Chronocort:IRHC). Before the study is initiated, the login information and instructions for use of the IRT will be provided to each site. The randomization list will be generated by the study statistician using a computer-generated central randomization list using balanced blocks. Randomization will be balanced

within site and stratified by the participant's fludrocortisone replacement status (requires fludrocortisone or does not require fludrocortisone).

Participants will be allocated an identifying number sequentially per site at the screening visit (Visit 1) in the following format: Study No.-Site No.-Screening No. (e.g. [REDACTED], [REDACTED] etc. for site 1; [REDACTED] etc. for site 2). When the participant is randomized at the baseline visit (Visit 2), a separate randomization number will be allocated, which will be used internally for the purposes of treatment allocation and stratum identification. The screening number will still be used for participant identification purposes, so there may be gaps in participant ID numbers for screen failures. Randomization numbers will be assigned sequentially within each stratum as soon as participants fully satisfy all of the inclusion and none of the exclusion criteria. Screening and randomization numbers once assigned to a participant must not be re-assigned to another participant. Re-screened participants should be assigned the same participant number as they were assigned during their initial screening visit.

Potential bias in this study will be reduced by the following steps:

- Records will be kept of any participants screened, whether or not they enter the study. This will enable an assessment of the representative nature of the participants randomized.
- Both study treatments will be over-encapsulated so that they look the same, so both the participant and the Investigator will not know which treatment group the participant has been randomized to.
- The titration of each participant's dose of study treatment will be the same in both arms and will be based on the adrenal insufficiency checklist and androgen sampling thus ensuring that opportunities for optimization and control of androgens are the same in both arms.

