- The dose titration decisions will be made by an independent blinded physician who will be unaware of the treatment allocation to each participant.
- The treatment packs for each participant will be pre-packed and packs issued by the IRT to ensure that each participant receives the correct number of active and placebo capsules. After each visit, new supplies will be provided to the participant that contain the same number of capsules as the previous supplies (with placebo capsules masking any changes), regardless of whether the dose was titrated or not, thus ensuring the participant is not aware of any dose changes.
- The primary endpoint is an objective biochemical measure that is not subject to bias.
- Efforts will be made to ensure that all participants remain in the study and are evaluable.
- There will be rigorous monitoring of sites to ensure compliance with all study procedures.
- The statistical analysis plan (SAP) will be completed before screening of the first participant to the study.
- Treatment will be allocated using block randomization. The block size will be determined by the statistician and will not be communicated to the study team.
- To minimize bias whilst the study is ongoing, the study team will remain blinded to aggregated and individual data prior to database lock and any data reviews will use a dummy randomization list with generic labels.

- Participants and Investigators will be requested not to reveal details of the study on social media.

The IRT will be programmed with blind-breaking instructions. In case of an emergency, the Investigator has the sole responsibility for determining if unblinding of a participant's intervention assignment is warranted. Participant safety must always be the first consideration in making such a determination. If the Investigator decides that unblinding is warranted, the Investigator should make every effort to contact the medical monitor prior to unblinding a participant's intervention assignment unless this could delay emergency treatment for the participant. If a participant's intervention assignment is unblinded, the Sponsor must be notified within 24 hours of this occurrence. The date and reason for the unblinding must be recorded.

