Appendix 5: Adrenal Insufficiency Checklist

*This questionnaire should be used to determine if symptoms of **under- or over-replacement of glucocorticoids** have occurred in the preceding 4 weeks. Symptoms unrelated to CAH, but due to other causes, e.g. nausea with migraine, should be recorded on the eCRF AE page.*

Date of assessment (mm/dd/yyyy):				
Please ask subject:		Have you experienced any of the following symptoms more than once per week in the last 4 weeks?		
Symptoms	Yes	If Yes, do you believe this to be related to under or over replacement of glucocorticoid? Please state over/under.	No	Any clinically significant findings? Y/N
Sudden weight loss				
Sudden weight gain				
Lack of appetite				
Increased appetite				
Nausea				
Vomiting				
Headache				
Blurred vision				
Fatigue				
Weakness				
Dizziness				
Lightheadedness				
Syncope (sudden loss of consciousness)				
Sleeping difficulties				
Increased acne				
Other				
If yes to Other please specify:				

Version FINAL 1.0 – 01 Sept 2015

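### After each titration visit the diary asks for the dose of the 'revised' medication, an entry that a blinded participant either cannot answer or can answer only by learning of a dose change

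*Protocol*

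**What the plan says.** Protocol Section 8.1.3 describes supply after Visit 3. Packs keep the same capsule count, with placebo making up any difference, "thus ensuring the participant is not aware of any dose changes". The next sentence asks participants, in the electronic diary, to "record the dose, date and time they took the first dose of the revised study medication (if applicable". Sections 8.1.5 and 8.1.7 repeat the pair after Visits 4 and 5.

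Section 6.3 says that new supplies with an unchanged capsule count follow each visit "regardless of whether the dose was titrated or not, thus ensuring the participant is not aware of any dose changes". It also says "Both study treatments will be over-encapsulated so that they look the same". Under Section 4.2 the independent blinded physician enters the titration decision in the IRT, which tells the pharmacist what to dispense.

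Participants' symptoms enter the titration rules. The Appendix 5 checklist is put to the participant ("Have you experienced any of the following symptoms more than once per week in the last 4 weeks"). Section 4.2 states: "Clinical symptoms of adrenal insufficiency on the adrenal insufficiency checklist should take precedence over androgen results and would inhibit titration". If signs of under-replacement persist after at least one reduction, "a reversion to the previous dose is permitted (i.e. an increase of 5 mg) after discussion with the medical monitor"; if they still persist, study treatment is stopped.

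Dose is a component of the biochemical and dose responder definitions (Sections 9.1.1 and 9.1.2) and is itself the second key secondary endpoint (Section 9.1.3).

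**The concern.** The masking sentence and the diary sentence stand next to each other and pull in opposite directions. If the prompt appears only after a change, it tells the participant that a change was made. The only scheduled change is a 5 mg reduction, and a reduction requires 17-OHP below 300 ng/dL and A4 below the sex-specific limit (Section 4.2). A participant who learns of a reduction therefore learns something about their androgens. The protocol guards that information elsewhere: Section 5.3 bars androgen testing outside study visits, and Section 8.1.13 treats local androgen analysis as unblinding.

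The same participant then answers the checklist, completes the SF-36, MAF, EQ-5D-5L and VAS scales, and decides on stress dosing, which Section 6.1.1 allows without authorization. Section 6.3 describes the primary endpoint as an objective biochemical measure free of bias, but its dose component depends partly on reported symptoms.

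**Working it through.** **1. Whom does the diary entry address?**
- If 'revised' meant any new pack, the entry would apply to everyone, because Section 6.3 supplies everyone after each visit and Section 4.2 has all participants telephoned a week after receiving new packs. The qualifier 'if applicable' would then exclude nobody.
- The baseline entry in Section 8.1.2, which does apply to everyone, asks participants to "record the dose, date and time they took the first dose of study medication (Chronocort or IRHC" and carries no such qualifier.
- Read literally, the later entry therefore picks out participants whose dose changed.

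**2. Can such a participant answer it?** Capsules look alike and counts are constant, so a participant masked as described does not know the mg dose after titration. The entry is left blank, guessed, or completed from information that the blind withholds. Diary screens and pack labels are not in the documents, so the text cannot settle which.

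**3. If a reduction is disclosed, which endpoints can move?** A participant prompted by a reduction is already at 25 mg or less.

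| Route | Biochemical response | Dose response | Mean daily dose |
|---|---|---|---|
| Further reduction blocked by symptoms | no change | no change | higher by 5 mg for that participant |
| Reversion from 25 to 30 mg | lost only if in control at baseline (others are allowed 30 mg) | lost | higher by 5 mg |
| Withdrawal from treatment | lost (Section 9.4.2.1) | lost (Section 9.4.2.2) | handled in the repeated measures model |

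The dose is meant to stay fixed after the Week 16 titration (Section 4.1), so feedback into scheduled titration concerns the prompts after Visits 3 and 4.

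**4. Scale.** Inputs from Protocol Section 9.2: 25 per arm, 40% on IRHC, 68% on Chronocort, margin 15 points, one-sided 2.5%, continuity-corrected z-test with unpooled variance.

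Plan's own figure first:
- SE = √(0.40×0.60/25 + 0.68×0.32/25) = 0.1353
- Power = Φ((0.68 − 0.40 + 0.15 − 1/25)/0.1353 − 1.96) = 82.2%, which agrees with the stated 80% or more. Exact binomial enumeration of the same test gives 79.8%.

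One participant:
- Responder rate: 1/25 = 4 percentage points in that arm.
- Raw mean dose: 5 mg/25 = 0.2 mg in that arm.

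The documents give no number of affected participants, so the following is an assumed range. If the expected number of Chronocort responders falls by 0, 1, 2 or 3 of 25, the same formula gives power of 82.2%, 72.3%, 60.9% or 49.0%.

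**The case against.** The strongest reply is that no passage says participants are told of a change. They 'will be asked to' make an entry. The titration decision runs from physician to IRT to pharmacist, and the packs are masked. The baseline entry also asks for a dose, although everyone starts on 30 mg and there is nothing to reveal, which suggests template wording. A diary that asks everyone about the first intake from each new pack would disclose nothing. This stands as a limit on what can be claimed: disclosure is possible, not shown. It does not reconcile the two sentences, because the loose reading leaves 'if applicable' without work to do and still asks for an unknown mg dose.

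Three stronger readings are tempting, and the documents do not support them.

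- *The prompt reveals the arm.* A reader might take 40% of IRHC participants as down-titrated (SAP Section 3) and 68% of Chronocort participants, and compute 17/(17 + 10) = 63% Chronocort among those prompted. The 68% is a Week 28 response rate with a 17-OHP limit of 1200 ng/dL, and it includes some participants still on 30 mg. It is not a Week 4 titration share. With equal shares the figure is 50%. Knowing of a change does not by itself identify the arm.
- *A blocked further reduction costs a responder.* It does not, by the table above; it can move only the mean dose.
- *The effect favors Chronocort.* If more Chronocort participants were reduced, expectation-driven reversions would fall mainly on that arm and count against it. The direction is not established.

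**Conclusion.** The point holds as an internal contradiction in Protocol Sections 8.1.3, 8.1.5 and 8.1.7, set against Section 6.3. Read literally, the diary entry is either unanswerable under the blind or discloses a dose change. Whether it did either in practice depends on diary screens and labels that the documents do not contain.

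If it discloses, responder status is exposed only through a reversion from 25 to 30 mg or withdrawal from treatment. Mean daily dose is also exposed to blocked reductions, and participant-reported outcomes and stress dosing are exposed directly. Each affected responder is worth 4 points in an arm of 25; the number affected is unknown, so no overall bias can be stated. The plan's sample size figure is unaffected. The correction is worth making because it costs almost nothing and protects a component of the primary and both key secondary endpoints.

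**What to change.** In Sections 8.1.3, 8.1.5 and 8.1.7, have every participant record the date and time of the first capsules taken from each new pack, and delete 'dose', 'revised' and '(if applicable)'. Take the mg dose from the IRT, which already holds each decision. Take the effective date from the diary entry, not from IRT pack assignment, because packs are shipped or collected afterwards.

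Confirm that diary prompts and pack labels are identical whether or not the dose changed. SAP Version 4.0 followed a blinded data review before database lock, so for participants already treated this check is what remains useful; its answer should be reported in the CSR.

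Changing the first-dose entry in Section 8.1.2 is optional tidying: everyone starts on 30 mg, so no dose change can be revealed there.

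The cost is a wording change in the protocol and diary and one check of the diary build and labels. No dosing rule changes and no dose data are lost.
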